**Table 4 - Search list for invasive gynecologic surgery**

Terms
Endometrial Ablation
Hysterectomy; subtotal (only uterus removed)
Hysterectomy; Total (uterus and cervix removed)
Hysterectomy; Radical (uterus, cervix, ovaries, oviducts, lymph nodes, & lymph channels removed)
Unilateral/bilateral Salpingectomy(excision of the fallopian tube)
Partial Salpingectomy
Unilateral/bilateral Oophorectomy (excision of the ovary) or removal of the ovarian cyst
Unilateral/bilateral salpingoophorectomy (excision of the ovary and fallopian tube)
Cornual resection
Diagnostic laparoscopy
Salpingotomy
Operative hysteroscopy and specify
Surgery for vascular injury, specify
Surgery for visceral organ injury, specify

Besides all these items from additional pelvic/abdominal surgery eCRF, the following situations will also be considered as invasive gynecologic surgery.

If a subject had Essure removal using Salpingectomy, Hysterectomy and Cornual resection, she will be considered as having invasive gynecologic surgery and classified as “Essure removal using invasive gynecologic surgery”. If a subject had laparoscopic tubal sterilization after she had Essure attempt, she will be considered as having invasive gynecologic surgery and classified as “laparoscopic tubal sterilization after Essure attempt”. If a subject had Essure attempt after she had laparoscopic tubal sterilization, she will be considered as having invasive gynecologic surgery and classified as “operative hysteroscopy, Essure placement after laparoscopic tubal sterilization”.

#### **6.4.1 Subject Incidence**

The subject incidence is defined as the number of subjects with at least one event divided by the number of subjects at risk. Subject incidence will be calculated for each group. The risk difference between two groups will also be calculated. Its associated 95% CI will be derived based on normal approximation.

Additionally for the main endpoints, subject incidence and risk differences will be given for the following time intervals: Day 0, Day 1-7, Day 8-30, Day 31-90, Day 91-180, Day 181-365, Day 366-730, > Day 730.

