### **4.3 Handling of loss to follow-up, premature discontinuation, and censoring**

Subjects who leave the study before reaching the study completion assessment five years after start of the sterilization procedure will be included in the analysis populations, since the analyses are based on all subjects who attempt sterilization.

For subjects who attempt two sterilization methods, or have any hysterectomy (subtotal, total or radical), or have Essure complete removal using a salpingectomy, or device removal not accompanied by sterilization procedure, their data will be censored for analysis purpose on the earliest date of second sterilization method, hysterectomy surgery date, or Essure removal date, for the primary analysis.

Data will be collected for all the subjects until the end of study or early termination.

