## 6.4 Outcome endpoints and variables

The main objective of this observational study is to evaluate under routine clinical practice conditions the incidence of important treatment-emergent AEs under hysteroscopic sterilization (Essure) and laparoscopic tubal sterilization. An AE is considered as treatment-emergent when it starts or worsens on or after the index date and up to the date of subject withdrawal or the censoring date, as described in Sections 4.3 and 6.1.3.

The outcome endpoint and variables are presented in Table 2. The descriptive analysis will be performed for all the variables listed below and the comparative analysis will be performed only for the main endpoints.

For the main endpoints, the subject incidence (regardless of the time each subject is “at risk”) is the number of subjects with treatment-emergent events divided by the number of subjects at risk.

Laboratory evaluation results will be compared to their normal ranges. Any values out of normal ranges will be identified. The change from baseline for each laboratory parameter will also be presented for each post-baseline visit.

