#### **6.4.2 Exposure-adjusted subject incidence**

The exposure-adjusted subject incidence is defined as the number of subjects with at least one event divided by the total time at risk. For the subject who has at least one event, the risk duration is from the index date to the date of the first event. For the subject who has no events reported, the risk duration is from the index date to the censoring date or end of study date. The exposure adjusted incidence will be calculated for each group. The difference between two groups and its associated 95% CI will be calculated using the method proposed by Liu et.al (2006) [1].

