#### **6.4.3 Kaplan-Meier estimates**

Kaplan-Meier estimates for the main endpoints will be given in tables and figures describing the time course until the first event of interest. Subjects who did not experience the event until end of observation are right-censored, see also Section 6.1.3.

Confidence intervals are based on asymptotic method for standard error estimation by Greenwood (1926) [2].

The x-axis of the Kaplan-Meier figures will be restricted to the period in which at least 10% of the subjects are at risk as suggested by Pocock et al. (2002) [3].

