#### **6.4.4 Hazard ratios**

Hazard Ratios will be derived for the main endpoints from Cox proportional hazard model with treatment group as an independent variable. Other covariates could include, but are not limited to age, BMI, race, hormonal contraception used at baseline and appropriate pre-existing conditions (bleeding disorder, ovarian pathology, etc.).

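### None of the four measures planned for each main endpoint is named primary, and the only risk contrast with a stated confidence interval ignores follow-up time, so unequal drop-out could bias it

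*SAP*

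**What the plan says.** The protocol synopsis words the main AE, adjudicated and surgery endpoints as proportions of subjects, evaluated through 60 months. The SAP plans four measures for them:

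- **Crude subject incidence (6.4, 6.4.1).** This is "the number of subjects with treatment-emergent events divided by the number of subjects at risk". The definition opens "For the main endpoints, the subject incidence (regardless of the time each subject is" and goes on to say that time at risk plays no part. On the contrast: "The risk difference between two groups will also be calculated. Its associated 95% CI will be derived based on normal approximation". In addition, "subject incidence and risk differences will be given for the following time intervals: Day 0, Day 1-7, Day 8-30", and so on up to one open interval after Day 730.
- **Exposure-adjusted incidence (6.4.2).** The denominator is total time at risk. "The difference between two groups and its associated 95% CI will be calculated using the method proposed by Liu" and co-authors.
- **Kaplan-Meier (6.4.3).** "Kaplan-Meier estimates for the main endpoints will be given in tables and figures", with Greenwood intervals. No between-group difference and no time point are given.
- **Cox hazard ratio (6.4.4).** The covariate list is open: "Other covariates could include, but are not limited to age, BMI, race" and further items.

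The SAP attaches the word primary to the adjusted full analysis set (5.1, 6.6.2) and to the censoring rule (4.3, 6.1.3), never to a measure. Section 4.3 covers drop-outs: "Subjects who leave the study before reaching the study completion assessment five years after start" of the procedure stay in the analysis populations. The one sensitivity analysis (6.8) lifts the planned censoring events and does not address drop-out.

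**The concern.** A woman lost at month 12 without an event stays in the crude denominator and contributes nothing to the numerator, exactly like a woman observed event-free for five years. With equal drop-out, both arms are understated to a similar degree. With unequal drop-out, the arm that loses more women has the lower crude proportion even when the true risks are the same.

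Unequal drop-out is plausible here. The study is open-label and non-randomised and lasts five years. SAP section 7 anticipates drop-out, and SAP section 4 expects media attention to make the groups differ. In a safety comparison the costly direction is a real excess that shrinks in the reported risk difference. Because no measure is ranked, the report could also lead with whichever of four partly disagreeing estimates reads best.

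**Working it through.** The documents give no sample size, event rate or drop-out rate, so there is no figure of the plan's own to reproduce. Everything below rests on assumed inputs.

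**Inputs from the documents:** 5 years of follow-up (protocol synopsis); 1:1 matching in the primary set (SAP 6.6.1); 95% intervals (6.4.1).

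**Assumed:** 300 per arm; equal true 5-year risk *p* in both arms; drop-out *d* by year 5, unrelated to the event; exponential event and drop-out times.

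**Formulae.** Event hazard l = -ln(1-p)/5 and drop-out hazard c = -ln(1-d)/5. The expected crude proportion is l/(l+c) × [1 - (1-p)(1-d)].

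**Worked case,** p = 30%, drop-out 50% (Essure) v 20% (laparoscopic):

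- l = 0.0713. Essure c = 0.1386; laparoscopic c = 0.0446.
- Essure: 0.0713/0.2100 × (1 - 0.70×0.50) = 0.3398 × 0.65 = 22.1%.
- Laparoscopic: 0.0713/0.1160 × (1 - 0.70×0.80) = 0.6152 × 0.44 = 27.1%.
- Difference -5.0 points, although the true difference is 0.
- Standard error = √[(0.221×0.779 + 0.271×0.729)/300] = 3.5 points, so the 95% interval excludes 0 in about 29.5% of studies.

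**Range,** crude difference in points (share of studies whose interval excludes 0):

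| True risk | 30% v 20% | 40% v 20% | 50% v 20% |
|---|---|---|---|
| 5% | -0.3 (5.3%) | -0.6 (6.4%) | -0.9 (8.4%) |
| 10% | -0.5 (5.6%) | -1.1 (7.8%) | -1.7 (12.1%) |
| 20% | -1.1 (6.4%) | -2.2 (11.1%) | -3.4 (20.3%) |
| 30% | -1.6 (7.2%) | -3.2 (14.8%) | -5.0 (29.5%) |

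With 25% drop-out in the laparoscopic arm and p = 26%, the shift is -2.1 points at 40% Essure drop-out (about 10% exclusion) and -3.7 points at 50% (about 20%).

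**A true excess can be hidden.** With true risks of 25% v 20%, the crude difference is 4.5 points at equal 20% drop-out, 1.8 at 40% v 20%, and 0.3 at 50% v 20%.

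**The other planned measures.** I simulated 4,000 studies per scenario with true risk 20% or 30% and drop-out 40-50% v 20%, using a simple Wald interval for the rate difference in place of the SAP's cited method.

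- Constant hazard: the rate difference is unbiased (4.4-5.0% exclusion) and so is the Kaplan-Meier 5-year difference (4.7-5.5%, mean within 0.1 point of 0).
- Falling hazard (Weibull shape 0.5): the crude difference is -1.5 to -3.4 points (7-17% exclusion). The rate difference drifts the other way, by +0.24 to +0.63 per 100 person-years (6.6-9.1%). The Kaplan-Meier difference stays within 0.1 point of 0.
- True risks 30% v 20%, constant hazard, drop-out 50% v 20%: crude 4.1 points, Kaplan-Meier 10.1.

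**Limit of Kaplan-Meier.** SAP 6.4 counts pain as chronic only after more than 182 days, so a woman who leaves soon after pain starts cannot become a case. Adding that rule to the simulation leaves Kaplan-Meier differences of about -0.3 to -1.3 points under equal true hazards. That is smaller than the crude shift, but not zero.

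**The case against.** **Three of the four measures use follow-up time.** This stands. The rate difference in 6.4.2 is an absolute contrast with a 95% interval and a time-at-risk denominator, and Kaplan-Meier and Cox are also planned. A reader might infer that drop-out can decide the study's answer, but the documents do not support that: it can shift one of four reported measures. The rate difference is still not a full substitute, because it describes a rate while the endpoints are proportions, and it is reliable under unequal drop-out only if the hazard is roughly constant.

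**The crude difference is not declared the lead result.** This also stands. The wording of the endpoints may lead a reader to treat it as the default, but no section ranks it, and protocol 10.3 lists incidence rates and proportions side by side.

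**The study is exploratory.** Both documents disclaim confirmatory tests and expect channelling bias that no analysis can overcome. That settles multiplicity. It does not correct an estimator, or stop one estimate from being emphasised over another. The exclusion percentages above are a gauge of how large the shift is relative to its interval, not type I error rates for a planned test.

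**The size depends on the inputs.** Conceded. Protocol 9.6.1.1 expects very few autoimmune cases, and the shift for such an endpoint is negligible.

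**Interval-specific differences help.** They would only if each interval's denominator were the women still at risk at its start. The SAP does not define this, and the last interval pools about three of the five years.

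**Conclusion.** The point holds in limited form. No effect measure is primary, and the only risk contrast with a stated interval is biased if drop-out differs by arm, towards making the arm with more drop-out look safer. With common endpoints (true risk 20-30%) and drop-out of 40-50% v 20-25%, the shift is about -2 to -5 points, and the interval excludes zero in about 10-30% of studies at 300 per arm. It is under 2 points for a 10-point drop-out gap or a rare endpoint. These figures assume drop-out unrelated to the event. As the documents give neither drop-out nor event rates, the bias is a possibility, not a finding about this study. The consequence is a biased or selectively emphasised estimate. This is a cheap improvement to the plan, not a flaw that invalidates it.

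**What to change.** In SAP 6.4:

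1. Name one primary contrast for each main endpoint: the Essure minus laparoscopic difference in Kaplan-Meier cumulative incidence, in the Adjusted Full Analysis Set.
2. Fix the time point so that the 60-month visit window (-4 weeks, +1 week) supports it. Protocol 9.2.2.11 ends data collection once that visit is complete, so women seen early in the window are censored before 60 months. One option is the day the window opens: 5 × 365 - 28 = Day 1797.
3. Give a 95% interval from a variance that respects the 1:1 matching, for example a bootstrap of matched pairs.
4. Label the crude difference, the rate difference and the hazard ratio as supportive.
5. State that the Kaplan-Meier difference assumes that drop-out and the planned censoring are non-informative, and that drop-out also truncates ascertainment of chronic pain. The change reduces the bias but does not remove it.

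The cost is SAP wording, one extra estimate per endpoint from data already collected, and a slightly wider interval than the crude one.

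Two optional reporting changes do not rest on the calculation above: fixing the Cox covariates in 6.4.4, and splitting the interval after Day 730 by year. If the covariates are fixed, first reconcile SAP Table 5 with protocol 10.3, which lists pre-existing pain disorders that Table 5 omits.

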- **Hypersensitivity / allergy:** The proportion of subjects with adjudicated new onset or worsening allergic / hypersensitivity reactions (e.g., urticaria, rash, itching, as well as other symptoms that may be related to inflammation). For potential allergic / hypersensitivity reactions, investigators will be instructed that an evaluation per standard medical practice must be performed in any subject presenting with urticaria, angioedema, unexplained rash, or unexplained itching. Evaluation will also be performed in subjects who present with other symptoms that could possibly be related to an inflammatory reaction (e.g., hair loss, fatigue, muscle pain, joint pain). Supplemental PRO Questionnaires will be used in both groups to actively solicit for such events. In addition, this evaluation will include collection and submission of blood and serum or plasma samples to a central laboratory for a nickel lymphocyte proliferation test (NiLPT), which is a measure of sensitization to nickel, a chromium lymphocyte proliferation test (LPT), which is a measure of sensitization to chromium, serum or plasma nickel level, serum or plasma titanium level, and inflammatory cytokines panel.

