For autoimmune disorders, any subject presenting with symptoms indicating a potential autoimmune disorder should be evaluated per standard medical practice. All effort will be made to obtain records of any diagnostic workup conducted by outside physicians. A NiLPT, chromium LPT, serum or plasma nickel level, and serum or plasma titanium level and serum inflammatory cytokines will also be drawn by the study site. An appropriate human leukocyte antigen (HLA) panel will be run on previously obtained baseline samples if sufficient sample exists. An additional whole blood sample will be drawn for HLA if needed. Frozen serum will be used in cases of suspected autoimmune disorders (for both the index case as well as a randomly selected control group). If sufficient frozen sample exists, it will be adequate to be used for tests used to diagnose autoimmune conditions (e.g., anti-citrullinated protein antibody in cases of suspected rheumatoid arthritis, thyroid peroxidase antibody for suspected autoimmune thyroid diseases, and antinuclear antibody in cases of suspected lupus erythematosus). Based on epidemiology, the number of subjects who develop an autoimmune disease during the study is expected to be very small. If removal of a device or any other surgery is performed, pathological evaluation and metallurgic studies (if applicable) will be included.

After the evaluation of the subject is complete, regardless of investigator's assessment as to whether or not an autoimmune disorder exists, all information will be forwarded to the adjudication committee in a blinded fashion. In cases of pathological evidence, blinding may not be possible. Final determination of whether or not an autoimmune disorder has occurred will be based on the determination of this committee. Once adjudicated events are available, the following comparisons will be possible:

- Pathological findings (if sufficient specimens are obtained) in subjects with Essure and adjudicated autoimmune disorders can be compared to pathological findings in subjects with Essure without autoimmune disorders as well as to pathological findings in laparoscopic tubal ligation subjects (with and without adjudicated autoimmune disorders).

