## **5 Analysis sets**

### **5.1 Assignment of analysis sets**

The goal of this study is to assess the various aspects of safety of the procedures studied. Assuming there is adequate overlap in the PS distribution to enable comparisons in the PS confounder-adjusted population between treatment groups, the adjusted full analysis set will be the primary analysis set.

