## Adjusted reliance set

Among the propensity score confounder-adjusted population, a subject will be included if both she and her matched partner are included in the Reliance Set.

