**Table 5 - Baseline variables suspected to be included in PS modela**

Variables
Age
Race
BMI
US Geographical Region
Insurance type (Government-subsidized program, Commercial/Private , Other)
Hormonal Contraception Use At Baseline
Pre-existing abnormal uterine bleeding
Disorders associated with hysterectomy (fibroids, ovarian pathology, endometriosis, prolapse, hyperplasia)
GI disorders (e.g., IBS)
Pre-existing Autoimmune Disease
Pre-existing Diabetes
Pre-existing Hypertension

a Based on internal data on file

The approach to take would be to first construct the PS model and estimate the PS in both groups, assess the overlap, and determine if a PS confounder-adjusted analysis can proceed based on the overlap.

Logistic regression will be used to model the relationship between the background variables and the treatment, and a PS will be estimated for each subject by a fitted value from the logistic regression.

In an effort to improve model fit several steps can be investigated, including dichotomization or grouping of baseline variables intended for inclusion in the model.

In a first step, all above listed potential confounders are to be included in the stepwise model build procedure.

In a second step, all other baseline data plus the list of potential confounders used for model build in the first step will be included in a stepwise logistic regression procedure.

The two models will be compared. If the contribution of the additional data is low, the PS built on the first model will be considered for analysis. The independent party will assess this and propose the final model. This proposal will be discussed with the FDA.

Use of 1-to-1 nearest neighbor matching with a caliper of 0.2 SD of the logit Propensity Score will be the preferred procedure in order to ensure comparability. (Austin 2011 [5], Rosenbaum and Rubin 1985 [6])

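### The normal-approximation interval for the risk difference has no rule for sparse counts, and shrinks to zero width if neither arm has an autoimmune event

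*SAP*

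**What the plan says.** SAP 6.4.1 defines subject incidence, takes the risk difference between the groups and adds one sentence on precision: "Its associated 95% CI will be derived based on normal approximation". No alternative is named for small counts. The section also asks for incidence and risk differences in eight intervals ("Day 0, Day 1-7, Day 8-30, Day 31-90, Day 91-180, Day 181-365, Day 366-730, > Day 730"), without saying whether these carry confidence intervals.

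SAP Table 2 lists newly diagnosed autoimmune disorder among the main endpoints. Protocol 9.6.1.1 says that "the number of subjects who develop an autoimmune disease during the study is expected to be very small". Neither document gives an expected rate or a fixed sample size; Protocol 10.4 and SAP 4.1 tie enrollment to the availability of Essure, with about two laparoscopic subjects per Essure subject.

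On matching, SAP 5.1 states that, given adequate overlap of the scores, "the adjusted full analysis set will be the primary analysis set". SAP 6.6.1 says "Use of 1-to-1 nearest neighbor matching with a caliper of 0.2 SD of the logit Propensity Score will be the preferred procedure", and the adjusted reliance set is defined by pairs: "a subject will be included if both she and her matched partner are included in the Reliance Set". For the hazard ratio, SAP 6.4.4 says "Hazard Ratios will be derived for the main endpoints from Cox proportional hazard model with treatment group as an independent variable", with optional covariates. Neither 6.4.1 nor 6.4.4 names a variance method for matched data.

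**The concern.** A normal approximation builds its standard error from the observed proportions. When both are zero the standard error is zero, and the table would show a difference of 0.0% with limits 0.0% and 0.0%. That asserts certainty when the data contain almost no information. The autoimmune endpoint is where this is most likely, and the study was ordered by the FDA to examine safety questions of this kind. SAP 6.4 reserves comparative analysis for the main endpoints, and this is the only interval that 6.4.1 attaches to the risk difference. A zero-width or too-narrow interval could be taken for evidence that the groups do not differ.

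The missing matched-data variance is a different matter. It leaves the primary analysis under-specified: two programmers could both follow the text and produce different intervals.

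**Working it through.** The documents state no sample size, rate or event count for these endpoints, so there is no figure of the plan's own to reproduce. Assumptions: 150, 300, 500 or 1000 women per arm in a 1:1 matched set; autoimmune risks of 0.1% to 1%. The normal approximation is read as the Wald formula, its usual meaning.

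**1. No event in either arm**

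Wald: d ± 1.96·√[p₁(1−p₁)/n₁ + p₂(1−p₂)/n₂]. With p₁ = p₂ = 0 this is 0 ± 0 at any n.

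Newcombe: with no events each Wilson interval runs from 0 to z²/(n+z²), so the limits for the difference are ±z²/(n+z²). At n = 300 this is 3.84/303.84 = 1.26%. The chance of no event in either arm, at 0.1% risk in each, is 0.999^(2n). The exact (two-sided 95%) upper limit for one arm is 1 − 0.025^(1/n).

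| n per arm | Wald | Newcombe, points | Chance of 0 v 0 at 0.1% risk | Exact upper limit per arm |
|---|---|---|---|---|
| 150 | 0 to 0 | ±2.50 | 74% | 2.43% |
| 300 | 0 to 0 | ±1.26 | 55% | 1.22% |
| 500 | 0 to 0 | ±0.76 | 37% | 0.74% |
| 1000 | 0 to 0 | ±0.38 | 14% | 0.37% |

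The problem is not confined to zero. With 1 v 0 events at 300 per arm, Wald gives −0.32 to 0.99 points and Newcombe −0.96 to 1.86.

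**2. Coverage**

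Exact coverage sums the two binomial probabilities over all outcomes whose interval contains the true difference.

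| True risks | n = 150 | 300 | 500 | 1000 |
|---|---|---|---|---|
| 0.5% v 0.1%, Wald | 59.3% | 77.4% | 91.3% | 93.1% |
| 0.5% v 0.1%, Newcombe | 100.0% | 99.9% | 99.6% | 96.9% |
| 1% v 0.5%, Wald | 88.4% | 93.2% | 94.0% | 94.9% |
| 0.5% v 0.5%, Wald | 99.3% | 97.0% | 95.4% | 95.7% |
| 5% v 3%, Wald | 94.9% | 95.0% | 95.0% | 95.0% |

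The low values come largely from the zero-width interval, which misses any non-zero difference. At 0.5% v 0.1% and 300 per arm, 0 v 0 has probability (0.995 × 0.999)^300 = 16.5%, so coverage cannot exceed 83.5%. At 150 per arm the probability is 40.6% and the ceiling 59.4%.

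With equal risks in a 1:1 set the zero-width interval contains the true value, so coverage holds. In the unmatched set, 300 v 600 women at 0.5% each gives 91.4%.

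**3. Matching, a separate question**

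With equal risks and within-pair outcome correlation ρ, the paired variance is (1−ρ) times the independent-sample variance. An unpaired interval is therefore 1/√(1−ρ) times as wide as it should be: 1.026, 1.054 and 1.118 for assumed ρ of 0.05, 0.10 and 0.20. In a simulation of 1:1 caliper matching with no treatment effect (about 280 pairs), the ratio of unpaired to paired standard error was 0.00792/0.00789 = 1.004 at about 0.9% risk. It reached 0.04013/0.03497 = 1.15 only with common events and strongly prognostic covariates. The Cox model was not simulated.

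**The case against.** The strongest reply is that nothing formal rests on these intervals. The study is exploratory, has no margin or error rate to protect, expects confounding that analysis cannot remove, and SAP 4.2 names p-values, not confidence intervals, as its gauge of uncertainty. Counts and denominators will stand beside any degenerate interval, and SAP 6.4.2 provides a second between-group interval, for exposure-adjusted incidence, by its own cited method (not available here, so its behavior with sparse data is unknown). This limits the consequence. It does not make a 0-to-0 interval correct.

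Several stronger readings are tempting, and the documents do not support them:

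- **Allergy is also rare.** The remark about very small numbers concerns autoimmune disease only. Allergy has broad triggers ("Evaluation will also be performed in subjects who present with other symptoms that could possibly be related to an inflammatory reaction"), and at 5% v 3% the Wald interval is adequate.
- **The eight time intervals will be full of faulty confidence intervals.** SAP 6.4.1 promises risk differences there but does not say that intervals are printed, and no rates show that most cells are sparse.
- **Coverage is about 80% in general.** At 300 per arm, 1.0% v 0% does give 79.9%. But 0.985% v 0% gives 94.5% and 1.0% v 0.1% gives 94.3%, because the upper limit for one event (0.986%) just misses 1.0%. The 0 v 0 ceiling in the working does not depend on such a near miss.
- **The SAP prescribes unpaired intervals and a Cox model that ignores matching.** It is silent, 1:1 matching is only preferred, and the independent party must still report on overlap and the adequacy of the planned analyses.
- **Ignoring pairs makes rare-event intervals too narrow.** With positive correlation it makes risk-difference intervals too wide, and the effect nearly vanishes for rare events.

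It is also fair to say that the Newcombe interval is itself conservative here, covering 99.6% to 100% at 0.5% v 0.1% with up to 500 per arm.

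**Conclusion.** The point holds for the autoimmune endpoint and should be corrected. The zero-width interval at 0 v 0 is certain under the usual reading of the rule and needs no assumption about sample size. How often it occurs, and how far coverage falls, depends on arm sizes and rates that the documents do not give. The shortfall is large only with very low risks, modest arms and a true difference: 59% to 93% across the assumed sizes at 0.5% v 0.1%. It is slight at 1% v 0.5% from 300 per arm upward. Allergy and the time intervals come under the same concern only if counts there prove sparse and confidence intervals are printed.

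The unspecified matched-data variance is secondary. Its likely effect on the risk difference is an interval about 3% to 12% too wide at an assumed correlation of 0.05 to 0.20, mainly for common events. No size is claimed for the hazard ratio.

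**What to change.** In SAP 6.4.1, replace the normal approximation with a score-type interval for the risk difference (Miettinen-Nurminen or Newcombe). When neither arm has an event, also print the exact upper limit for each arm. State whether the eight time intervals carry confidence intervals; if they do, apply the same rule.

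For the adjusted sets, name the variance method. For the risk difference, use a paired score interval under 1:1 matching, or matched-set cluster-robust or bootstrap errors if the ratio varies or censoring leaves pairs incomplete. For the Cox model in 6.4.4, use a robust variance clustered on the matched pair.

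The cost is SAP wording and standard programming, with no new data. The downside is wider, somewhat conservative intervals for rare events.
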